15.4.2 Safety Data

The severity and frequency of adverse events, and laboratory data, physical exams, and vital signs, will be reported in tabular form. Adverse events will be coded using Medical Dictionary of Regulatory Activities (MedDRA) preferred terms and grouped by system, organ, and class (SOC). The frequencies of adverse events by type will be compared between study arms using Chi-square analyses; however, this analysis will be considered descriptive not inferential.

15.4.3 Descriptive Statistics

Summaries of the characteristics of the subject population in both groups at baseline will be prepared for both the ITT and evaluable subjects. A summary will be prepared to show dropouts/retention over time in each study group and for major subgroups. The number of missing observations will be compared between groups and for major subgroups. Weekly treatment retention will be presented. Investigational product compliance will be presented by investigational product reconciliation, and subject report of use.

15.4.4 Genetics Analyses

Genotyping and Association Analysis. Association analysis for either single or multiple SNPs (as a block) from GeneChip® Mapping 500K Array will be conducted by using the ALLELLE, CASECONTROL and HAPLOTYPE procedures of SAS/Genetics. The ALLELE procedure of the SAS/Genetics package can calculate descriptive statistics such as the frequency and variance of alleles and genotypes, as well as estimate measures of marker informativeness, test whether genotype frequencies are consistent with HWE (Hardy-Weinberg Equilibrium), and support three methods for calculation of the degree and significance of linkage disequilibrium (LD). Another useful procedure for the case-control design (as used in the current bupropion trial study) is CASECONTROL, which compares allele and genotype frequencies in bupropiontreated and placebo-treated groups using three types of Chi-square tests (i.e., genotype and allele case-control tests and linear trend test) and options for controlling correlation of allele frequencies among members of the same subpopulation. Similarly, we plan to test association using haplotype information from multiple SNPs within a candidate gene/region for the casecontrol data. The program to be used for this purpose is the HAPLOTYPE procedure of SAS/Genetics, which uses case-control data to calculate test statistics for the hypothesis of no association between alleles comparing the haplotypes and disease or invention group status. In addition, for the bupropion group, we also plan to examine the association between genetic markers and blood bupropion levels and safety outcomes such as frequency of severity of commonly reported AEs (e.g., insomnia). Furthermore, we plan to analyze interactions between significant genes or SNPs and environmental factors using a generalized multifactor dimensionality reduction method developed by Li and his colleagues at the University of Virginia.¹⁵³

Microarray Data Analysis. All microarray data generated from Affymetric Human Genome U-133 Plus 2.0 array will be subjected to a series of steps for normalization and filtering, which includes log-transformation, normalization within a slide, scaling among slides, and data filtering. To reduce individual variation, we will use expression profile of each subject prior to administration of investigational products as the baseline. All expression profiles of that individual at other time points will be compared with the baseline. After appropriate normalization, various statistical approaches will be applied to select genes differentially expressed in the bupropion and placebo groups. Computer programs written in SAS, Fortran, or MatLab for the traditional *t*-test, the SAM method (a modified *t*-test), variance analysis under a mixed model, and a mixture-model approach have been implemented in our laboratory and are ready for handling the data generated from this project. Given that each method has its own features, and there is no clear standard or consensus as to which method is preferable, we plan to use all of these methods to analyze each dataset. Only those genes that can be identified repeatedly by different methods will be selected for further characterization.

After differentially expressed genes are identified, we plan to use various clustering techniques over different experimental groups to analyze the expression patterns. Expression profiles will be grouped by: a) hierarchical cluster analysis using CLUSTER and TREEVIEW (http://rana.stanford.edu/software/), b) quality clustering (http://www.genome.org/cgi); and c) self-organizing maps (http://www-genome.wi.mit.edu/). The outputs from each program will be compared with respect to the clusters formed. These data will be used to determine relationships between the clusters, disease status, and intervention group and response. These methods have been routinely used in our microarray data analysis.^{68,154-156}

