2 STUDY SCHEMA

3 PROTOCOL SYNOPSIS

STUDY OBJECTIVES: The primary objective of this study is to assess the efficacy of bupropion in reducing methamphetamine use in subjects with methamphetamine dependence who report using methamphetamine 29 or less days during the 30 days prior to signing consent. It is hypothesized that bupropion, compared to placebo, will be associated with an increase in the proportion of subjects who achieve abstinence (confirmed by at least two methamphetaminenegative urines and no methamphetamine-positive urines) each week during the last two weeks (Weeks 11 and 12) for non-daily users. Secondary objectives include but are not limited to: assessing the success or failure to achieve abstinence (confirmed by at least two methamphetamine-negative urines and no methamphetamine-positive urines) each week during the last two weeks (Weeks 11 and 12) for subjects using methamphetamine 18 or less days during the 30 days prior to signing consent, assessing the safety of bupropion in this study population, assessing other measures of efficacy of bupropion in reducing methamphetamine use or craving, and other psychological assessments of methamphetamine dependence. In addition, if efficacy findings are promising, preliminary evaluations of the genetic markers associated with a positive clinical outcome or predictive of bupropion safety and efficacy including associations with bupropion pharmacokinetics (PK) may be performed.

STUDY DESIGN: This is a double-blind, placebo-controlled, parallel-group design study in which, after an up to 4-week screening period which includes a 2-week baseline assessment period, 200 subjects will be randomly assigned in an approximately 1:1 ratio to either receive placebo or bupropion (100 subjects per group) daily for 12 weeks, with follow-up assessments weekly for 4 weeks after completion of study interventions. Adaptive randomization will be used to balance study intervention groups within each clinical site, based on methamphetamine use (18 or less days *versus* 19-29 days out of 30 days prior to signing consent), severity of depression symptoms [Hamilton Depression Rating Scale (HAM-D) score ≤ 12 *versus* >12], and presence of adult Attention Deficit/Hyperactivity Disorder (Adult ADHD Clinical Diagnostic Scale - ACDS).

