All AEs will be reported in tabular form, indicating the frequency of each type of event by study intervention group, and by the following demographic characteristics such as gender, ethnicity, age, duration of addiction, and all combinations of these characteristics.

Association analysis for either single or multiple single nucleotide polymorphisms (SNPs) (as a block) from GeneChip® Mapping 500K Array will be conducted by using the ALLELLE, CASECONTROL and HAPLOTYPE procedures of SAS/Genetics. CASECONTROL will also be used to compare allele and genotype frequencies in the bupropion and placebo groups using three types of Chi-square tests (i.e., genotype and allele case-control tests and linear trend test) and options for controlling correlation of allele frequencies among members of the same subpopulation. Similarly, we plan to test association using haplotype information from multiple SNPs within a candidate gene/region for the case-control data. In addition, for the bupropion group, we also plan to examine the association between genetic markers and trough plasma levels of bupropion and safety outcomes such as frequency of severity of commonly reported AEs (e.g., insomnia). Furthermore, we plan to analyze interactions between significant genes or SNPs and environmental factors using a generalized multifactor dimensionality reduction method. Conduct of these assays will be dependent upon favorable efficacy findings.

If differentially expressed genes are identified, we plan to use various clustering techniques over different experimental groups to analyze the expression patterns. Expression profiles will be grouped by: a) hierarchical cluster analysis using CLUSTER and TREEVIEW b) quality clustering and c) self-organizing maps. The outputs from each program will be compared with respect to the clusters formed. These data will be used to determine relationships between the clusters, disease status, and intervention group and response.

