The rationale for screening for genetic variants stems from family and twin studies suggesting that substance abuse and addiction are complex traits that are influenced by genetics, the environment and their interaction. Support for this concept is provided from a large study of twins, where the concordance rates of DSM-III-R-defined drug abuse or dependence for monozygotic twins were almost double the rates for dizygotic twins.⁵⁶ There are a number of plausible candidate genes for methamphetamine dependence — that is, genes likely to affect an individual's vulnerability to methamphetamine dependence. Among the candidate genes operative in addiction disorders are serotonin, norepinephrine, human γ -aminobutyric acid (GABA), glutamate, and opioid receptors, all of which modify dopamine metabolism and dopamine neurons. It has been proposed that defects in various combinations of the genes for these neurotransmitters result in a reward deficiency syndrome and that such individuals are at risk for abuse of the "unnatural rewards."⁵⁷

Already a number of genes have been identified that appear to be associated with a predisposition for methamphetamine dependence and psychosis including COMT,⁵⁸ the dopamine DRD4 receptor,⁵⁸ the μ -opioid receptor gene,⁵⁹ OPRM1, gamma-aminobutyric acid receptor gamma 2 subunit gene (GABRG2),⁶⁰ the prodynorphin gene,⁶¹ and the β -arrestin 2 gene.⁶² Thus, in this study, we plan to investigate the potential association of genetic variants of a number of genes with methamphetamine dependence. Given that only limited number of candidate genes have been investigated in their potential association with methamphetamine dependence, we plan to use Affymetric 500K Array set to identify susceptibility genes for methamphetamine dependence, with the special emphasis on those genes involved in the dopaminergic reward system, such as the genes encoding tyrosine hydroxylase, dopamine transporters, dopamine receptors, and monoamine oxidase A and B. Additional genes of interest include those encoding serotonin transporters, opioid receptors, and cannabinoid receptors.

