5.2 Secondary Objectives

Secondary objectives include but are not limited to:

- 1. Assessing the efficacy of bupropion in reducing methamphetamine use in subjects with methamphetamine dependence who report using methamphetamine 18 or less days during the 30 day prior to signing consent.
- 2. Determining the safety of bupropion in the study population.
- 3. Assessing the efficacy of bupropion in other measures of success in the reduction of methamphetamine use determined by methamphetamine qualitative and quantitative urinalysis, self-report of use, and combinations of the two.
- 4. Assessing the efficacy of bupropion in the reduction in the severity of methamphetamine dependence (assessed by ASI-Lite and self and observer scored CGI), craving (assessed by BSCS), ADHD symptoms, (assessed by AISRS scores), and severity of depression (assessed by HAM-D) as compared to placebo control.

- 5. Assessing the rates of continued abstinence 4-weeks after completing the investigational product dosing period.
- 6. Assessing the effects on HIV risk taking behaviors.
- 7. Assessing the effects of bupropion on study retention.
- 8. Evaluating genetic variance and change in expression profiles on clinical outcomes including efficacy and safety.
- 9. Assessing the association of BDNF levels with clinical success and the influence of bupropion on BDNF levels.

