12.3 Subject Randomization

Adaptive randomization using an interactive voice randomization system (IVRS) will be used to balance study intervention groups within each clinical site based on methamphetamine use (18 or less *versus* 19-29 days out of 30 days prior to signing consent), severity of depression symptoms (HAM-D score ≤ 12 *versus* >12), and presence of adult ADHD. The procedure allocates group assignment based on the assignments and prognostic variable levels for all previously randomized subjects. A new subject will be randomized with a "biased coin" procedure that uses randomization probabilities, favoring the treatment with the deficit enrollment, to improve the balance on group assignment.¹⁴³

When ready to randomize a subject, designated site staff will call the IVRS number and enter the information regarding each randomization variable presented above over the phone. These descriptors can then be used to randomize subjects into study intervention groups. Site staff enters relevant data using either the phone key pad or simple voice commands. The IVRS repeats the users' responses to verify entered data before saving and assigning an intervention group. The system allows the user to back up or re-enter data at any point prior to the intervention group assignment. The information is not finalized until the user reviews the entered data. Once the user has approved the information, the randomization algorithm is activated and an intervention group is assigned. All users are trained on the IVRS as part of the study training plan.

All randomization data are stored on the KAI network on a secure drive that is only accessible to a designated KAI network support staff member and the programmer responsible for programming the IVRS system. There is a physical firewall in place to prevent access to the KAI network via the Web. This limited access to randomization data is done to prevent inadvertent or unauthorized breaking of or tampering with the study blind.

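### Section 15.4.4 compares allele and genotype frequencies between the randomised arms, which cannot show whether genotype predicts response, and no genotype test stated there uses abstinence

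*Protocol*

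**What the plan says.** Protocol Section 15.4.4 (Genotyping and Association Analysis) names three SAS/Genetics procedures for the 500K array. It brings in one of them as follows: "Another useful procedure for the case-control design (as used in the current bupropion trial study) is CASECONTROL". The sentence goes on to say what is compared: "CASECONTROL, which compares allele and genotype frequencies in bupropiontreated and placebo-treated groups using three types of Chi-square tests". The synopsis commits to the same thing: "CASECONTROL will also be used to compare allele and genotype frequencies in the bupropion and placebo groups". The haplotype procedure in Section 15.4.4 tests the hypothesis of "no association between alleles comparing the haplotypes and disease or invention group status", where the penultimate word but one is evidently meant to be intervention. A later step examines interactions between environmental factors and whichever genes or markers come out significant.

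Two other genotype analyses are stated. Within the bupropion group, Section 15.4.4 relates markers to blood bupropion levels and to adverse events. Section 15.2.2 relates plasma bupropion to CYP 2B6 haplotype and to treatment success.

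The aims are different in kind. Secondary objective 8 (Section 5.2) is "Evaluating genetic variance and change in expression profiles on clinical outcomes including efficacy and safety". The synopsis seeks variants linked to good clinical outcome and to safety. Sections 4.1.9 and 15.2.2 hypothesise that BDNF 66Val homozygotes gain more from bupropion. Section 4.1.9 adds a separate aim: "we plan to use Affymetric 500K Array set to identify susceptibility genes for methamphetamine dependence".

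**The concern.** A case-control test is informative when case status could be associated with genotype. Here the two groups are the arms of a randomised trial. Allocation cannot depend on germline genotype and treatment cannot alter it, so the hypothesis of equal allele frequencies is true by construction. A significant marker would be a chance imbalance and would say nothing about who responds to bupropion.

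Two consequences follow. First, a planned analysis cannot serve the aim it sits under, and Section 15.4.4 states no other genotype test that uses abstinence. Second, the interaction step takes significant markers as its starting point, so chance imbalances could be carried forward as leads.

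**Working it through.** **1. Is genotype independent of arm?**
- Allocation is random (synopsis): "200 subjects will be randomly assigned in an approximately 1:1 ratio to either receive placebo or bupropion (100 subjects per group".
- Section 12.3: "The procedure allocates group assignment based on the assignments and prognostic variable levels for all previously randomized subjects". The balancing factors are site, methamphetamine use, HAM-D and adult ADHD. Genotype is not among them.
- The DNA sample is drawn during screening (Section 12.2), so having a sample cannot depend on the arm either.

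Hence P(genotype | bupropion) = P(genotype | placebo) for every marker.

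**2. The plan's own figures.** No sample size or power is stated for the genetics work. The success rates used below come from Section 15.5, whose calculation reproduces. With p1 = 0.238, p2 = 0.057, mean p = 0.1475, two-sided alpha 0.05 and power 95%:

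n = [1.96 × √(2 × 0.1475 × 0.8525) + 1.645 × √(0.238 × 0.762 + 0.057 × 0.943)]² / (0.238 − 0.057)² = (0.983 + 0.798)² / 0.0328 ≈ 97 per arm (108 with continuity correction), against the stated 100.

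At 100 per arm, exact power is 95.1% for Fisher's test and 96.8% for the Pearson chi-square.

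**3. What the between-arm test can detect.** A simulation used 20,000 trials per allele frequency and 100 subjects per arm. Placebo success was 0.057 whatever the genotype. Bupropion success was 0.057 plus a fixed step per allele, the step being (0.238 − 0.057) / (2 × allele frequency), capped at 1. This is deliberately extreme, because one marker carries the whole drug benefit.

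| Allele frequency | Trend test, arm vs arm, at 0.05 | Allele test, arm vs arm, at 0.05 | Genotype vs success, bupropion arm, at 0.05 | Same, at 1e-7 |
|---|---|---|---|---|
| 0.1 | 5.1% | 4.7% | 100% | 99.99% |
| 0.2 | 5.1% | 5.1% | 100% | 81% |
| 0.3 | 4.8% | 4.8% | 99.8% | 19% |
| 0.5 | 5.1% | 5.1% | 88.5% | 0.3% |

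The simulation error at 5% is √(0.05 × 0.95 / 20,000) = 0.15 percentage points, so both between-arm columns equal alpha. At 1e-7 the between-arm trend test rejected in no trial. Changing the threshold changes how many chance results appear, and cannot make any of them real.

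**4. Aims against stated genotype tests.**

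| Aim | Genotype test stated in Section 15.4.4 | Suited? |
|---|---|---|
| Response to bupropion (objective 8, BDNF 66Val) | Allele, genotype and haplotype by arm | No: abstinence is not used |
| Pharmacokinetics and safety | Markers vs blood levels and adverse events, bupropion group | Yes |
| Susceptibility to dependence | Haplotype by disease status | Only with non-dependent controls; none designated |

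**5. How much information a better test would have.** At the Section 15.5 rates, expected successes are 100 × 0.238 = 23.8 on bupropion and 100 × 0.057 = 5.7 on placebo. As an illustration, take an allele frequency of 0.3 in Hardy-Weinberg proportions (0.49, 0.42, 0.09). The placebo successes then split as 2.8, 2.4 and 0.5 across the three genotypes. Numbers fall further if some subjects decline genetics consent, which Section 14.3 allows. A genotype-by-treatment test would therefore have low power, and ordinary logistic regression would risk separation. The simulation in step 3 did not assess that interaction test.

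**The case against.** The case for leaving the text alone has several parts.

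- **The arm comparison may be an extra.** The synopsis states a general association analysis and then says CASECONTROL will also be used between arms. The phenotype of the general analysis is not named and could be left to a statistical analysis plan. This stands in part: the documents do not show that the arm comparison is the main genotype analysis. But Section 15.4.4 presents it as the use of CASECONTROL for what it calls the trial's case-control design, and Section 16.3 has the analysis follow the protocol's analytical plan. A comparison that is written down and wrong differs from a detail left open.
- **Response is addressed elsewhere.** The synopsis and Section 15.2.2 plan to relate genetics to outcome, and plasma bupropion to treatment success. A reader might infer that objective 8 goes wholly unexamined. The documents do not support that, since the safety part has a valid analysis and the link to response is announced. What is missing is any stated genotype test that matches it.
- **Susceptibility is not impossible.** Section 12.2 keeps DNA from screened subjects found ineligible, with substance-use history and MINI diagnosis, and some of them may lack a dependence diagnosis. This stands against any claim that the aim cannot be met. Still, they are not designated as controls, they are treatment seekers (Section 12.1), and every randomised subject is dependent (Section 9.1).
- **Little hangs on it.** The genetics work is called preliminary and depends on favourable efficacy findings. This limits the weight of the point and does not repair the comparison.

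**Conclusion.** The point holds. Section 15.4.4 and the synopsis specify a between-arm comparison of germline genotype whose power equals its type I error however strongly a marker predicts response. No genotype test stated in Section 15.4.4 uses abstinence. The bupropion-group analyses of blood levels and adverse events are sound within their scope. The conclusion rests only on randomisation and on genotype being fixed beforehand, and does not depend on the simulation's effect size.

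A reader might go on to infer that the plan, run as written, yields about 25,000 false-positive markers per test (500,000 × 0.05). The documents do not support this as a prediction. The marker count is read from the array's name, and the 5% level is set in the efficacy text (Section 15.4.1 and the matching synopsis paragraph), not for the array scan. The figure is illustrative only.

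The matter should be corrected before any genetic analysis is run. It does not touch the primary efficacy result or the safety conclusions.

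**What to change.** - In Section 15.4.4 and the synopsis, replace the arm grouping, including the intervention-group option in the haplotype test, with primary-outcome success versus failure, tested within the bupropion arm.
- Add a genotype-by-treatment test for the candidates the protocol already names (BDNF Val66Met, DRD2, COMT, CYP 2B6), adjusted for multiplicity and fitted by an exact or penalised method. The within-arm test alone cannot separate a marker of benefit from a marker of general prognosis.
- State that the interaction test has low power, with about 6 placebo successes expected.
- Label the 500K scan exploratory. Keep the between-arm allele comparison only as a check on randomisation or data quality, and do not let its results feed the interaction step.
- Remove the description of the trial as a case-control design.
- For susceptibility, either name a non-dependent control source or drop the claim.

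The response changes use the same samples and assays and cost only wording and analysis time. Naming controls for susceptibility could need further recruitment or external data; dropping that claim costs one exploratory aim.

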STUDY POPULATION: Two hundred treatment-seeking individuals with Diagnostic and Statistical Manual of Mental Disorders Fourth Edition (DSM-IV) criteria for methamphetamine dependence determined by Mini International Neuropsychiatric Interview (MINI) DSM-IV version will be randomized to receive either bupropion or placebo. Only those subjects who report 29 or less days of methamphetamine use in the 30 days prior to signing consent will be considered for enrollment. Males and females, 18 to 65 years-of-age, inclusive, with at least one methamphetamine-positive urine specimen provided during the screening or baseline period prior to randomization (or provide collateral information to verify recent use if a positive urine sample can not be obtained), who verbalize the ability to understand and provide written informed consent, will be included.

INTERVENTIONS: Subjects randomized to the bupropion group will receive 150 mg of sustained-release (SR) bupropion once daily for 3 days then twice daily, i.e., a total of 300 mg/day, for a total of 12 weeks (dose taper will be performed the last 3 days of the 12 weeks, to 150 mg per day). Subjects randomized to the placebo group will receive matched placebo tablets according to the same schedule. All subjects will receive two 60 minute early recovery group

sessions after signing consent but before randomization, and manual-guided group cognitive behavioral therapy (CBT) consisting of three 90 minute sessions/week during the 12 weeks of study interventions and once weekly during the 4 weeks of follow-up.

SAFETY ASSESSMENTS: All subjects enrolled in the study will have a physical examination, a 12-lead electrocardiogram (ECG), and clinical laboratory studies (blood chemistry, hematology, Hepatitis B and C virus serology, syphilis test, tuberculin test, and urinalysis) performed during screening. If the potential participant is female, a pregnancy test will also be performed during screening, on the first day of investigational product administration, at Study Weeks 4, 8, and 12 or earlier termination. Vital signs, concomitant medication use, and a urine screen for other substances of abuse will be assessed weekly during the study. Adverse events (AEs) will be assessed at each visit. At the end of the study, or if terminated early, subjects will be evaluated for AEs, vital signs, physical examination, clinical laboratory studies, and ECG.

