Insomnia. In the dose-response smoking cessation trial, 29% of patients treated with 150 mg/day of bupropion SR and 35% of patients treated with 300 mg/day of bupropion SR experienced insomnia, compared to 21% of placebo-treated patients. Symptoms were sufficiently severe to require discontinuation of treatment in 0.6% of patients treated with bupropion SR and none of the patients treated with placebo.

Neuropsychiatric Side Effects. In clinical trials with bupropion SR conducted in nondepressed smokers, the incidence of neuropsychiatric side effects was generally comparable to placebo. Depressed patients treated with bupropion in depression trials have been reported to show a variety of neuropsychiatric signs and symptoms including delusions, hallucinations, psychosis, concentration disturbance, paranoia, and confusion. In some cases, these symptoms abated upon dose reduction and/or withdrawal of treatment.

Antidepressants can precipitate manic episodes in bipolar disorder patients during the depressed phase of their illness and may activate latent psychosis in other susceptible individuals. The SR formulation of bupropion is expected to pose similar risks.

Cardiovascular Conditions. In clinical practice, hypertension, in some cases severe, requiring acute treatment, has been reported in patients receiving bupropion SR alone and in combination with nicotine replacement therapy. These events have been observed in both patients with and without evidence of preexisting hypertension. Data from a comparative study of ZYBAN, nicotine transdermal system (NTS), the combination of bupropion SR plus NTS, and placebo as an aid to smoking cessation suggest a higher incidence of treatment-emergent hypertension in patients treated with the combination of bupropion SR and NTS. In this study, 6.1% of patients treated with the combination of bupropion SR and NTS had treatment-emergent hypertension compared to 2.5%, 1.6%, and 3.1% of patients treated with bupropion SR, NTS, and placebo,

respectively. The majority of these patients had evidence of preexisting hypertension. Three patients (1.2%) treated with the combination of bupropion SR and NTS and 1 patient (0.4%) treated with NTS had study medication discontinued due to hypertension compared to none of the patients treated with bupropion SR or placebo.

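### Genetic markers of adverse events are examined in the bupropion arm alone, which cannot separate markers of a bupropion effect from markers of background events such as insomnia

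*Protocol*

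**What the plan says.** The synopsis (Study Objectives) describes the genetics work as "preliminary evaluations of the genetic markers associated with a positive clinical outcome or predictive of bupropion safety and efficacy", to be done if the efficacy findings are promising.

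For adverse events, the protocol names the arm twice. The synopsis (Analysis) states: "for the bupropion group, we also plan to examine the association between genetic markers and trough plasma levels of bupropion and safety outcomes". Section 15.4.4 states: "for the bupropion group, we also plan to examine the association between genetic markers and blood bupropion levels and safety outcomes". Both give insomnia as the example of a common event.

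No other part of the protocol tests markers against adverse events in placebo subjects or by arm:
- The case-control and haplotype procedures in Section 15.4.4 compare allele or haplotype frequencies between the randomized arms, which does not involve adverse events.
- The multifactor dimensionality reduction step concerns environmental factors and does not name treatment arm.
- Section 15.4.2 compares adverse-event frequencies between arms, but without markers.

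On background rates, Section 4.2.5 reports from a dose-response smoking-cessation trial that "35% of patients treated with 300 mg/day of bupropion SR experienced insomnia, compared to 21% of placebo-treated patients", and "29% of patients treated with 150 mg/day of bupropion SR". The dose in this trial is "i.e., a total of 300 mg/day, for a total of 12 weeks".

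**The concern.** A marker predicts the safety of a drug if the drug's effect on the event differs between carriers and non-carriers. An association within the treated arm mixes two things: the marker's relation to the event without drug, and any change in the drug's effect. With treated subjects only, the two cannot be separated. A variant that makes people sleep badly whatever they take would appear in the bupropion arm just as a variant that makes them sensitive to bupropion would.

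This matters most when the event is common without the drug. The event that the protocol names is of that kind: insomnia was frequent on placebo in the trial it cites, and Sections 4.1.5 and 4.1.6 list insomnia among the effects of methamphetamine itself. At stake is the reading of any safety marker found, since the stated purpose in Section 4.1.9 is to help individualize therapy.

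**Working it through.** **Inputs from the protocol.** Insomnia 35% at 300 mg/day, 29% at 150 mg/day and 21% on placebo (Section 4.2.5); 100 subjects per arm (Section 15.5). The protocol states no background share and no flag rate, so there is no figure of its own to reproduce on this point.

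**Step 1, background share.** Placebo rate divided by bupropion rate:
- at 300 mg/day: 0.21 / 0.35 = 0.60, with an excess of 0.35 − 0.21 = 0.14;
- at 150 mg/day: 0.21 / 0.29 = 0.72.

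These describe the smoking-cessation trial. The protocol gives no background rate for methamphetamine users in treatment.

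**Step 2, a marker that acts only on background insomnia (assumed).** Take 40% carriers. Two cases keep the placebo mean at 21%:
- 30% in carriers and 15% in non-carriers: 0.4 × 0.30 + 0.6 × 0.15 = 0.21;
- 33% and 13%: 0.4 × 0.33 + 0.6 × 0.13 = 0.21.

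Let the drug act independently of background and of the marker. Risk on drug = 1 − (1 − background)(1 − q), with q = 1 − 0.65/0.79 = 0.177, so that the arm averages 35%. The risks on drug become:
- first case: 1 − 0.70 × 0.823 = 42.4% in carriers and 1 − 0.85 × 0.823 = 30.1% in non-carriers;
- second case: 44.9% and 28.4%.

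In both cases the bupropion arm shows a clear marker difference (12 and 16 points), although the marker does not alter the drug's action.

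**Step 3, how often each test flags it.** Simulation with 100 genotyped subjects per arm, one marker, two-sided 5%. The one-arm test is a chi-square in bupropion subjects. The two-arm test is a Wald test of (risk difference on drug) − (risk difference on placebo).

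| Background risk, carriers / non-carriers | Bupropion only | Marker-by-arm, risk difference |
|---|---|---|
| 30% / 15% | about 24% | about 6% |
| 33% / 13% | about 39% | about 6% |

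If the drug instead adds a constant 14 points, the true contrast is exactly zero. The one-arm test then flags the marker in 32 to 54% of trials, and the contrast in 5 to 6%. Under independent action the true contrast is small but not zero (−2.7 and −3.5 points), which is why its rate is slightly above 5%. On the logit scale the contrast flags 7 to 10%, so the scale has to be named.

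**Step 4, the price for a real drug-specific marker (assumed).** Risks on drug 47% in carriers and 27% in non-carriers (0.4 × 0.47 + 0.6 × 0.27 = 0.35), and 21% in both on placebo. Power at 5% is about 54% for the one-arm test, about 35% for the risk-difference contrast and about 25% on the logit scale.

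**Step 5, availability of data.** DNA is drawn at screening from every subject who consents to genetics (Section 13.1 and Table 1). Adverse events are recorded at every visit in both arms (Table 1 and Section 14.6).

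**The case against.** The best defense is that the treated arm is the right place for part of this work. Sections 4.1.9 and 15.2.2 propose that variation in CYP 2B6 alters bupropion clearance and that slow clearance could explain toxicity. The protocol pairs blood levels with safety outcomes in one sentence. A chain from marker to level to adverse event can be studied only in people who take the drug, and the level itself helps to tell drug-mediated markers from others. This stands. It is a reason to keep the bupropion-arm analysis, but not a reason to leave out the placebo comparison.

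The objections to the size also stand:
- The 60% is borrowed from smokers. A reader might take it as this trial's figure; the protocol does not say so.
- The flag rates are for one large-effect marker at nominal 5% with everyone genotyped. Section 14.3 makes genetics consent optional, although inclusion criterion 6 in Section 9.1 lists consent for both parts. With 50 per arm the one-arm rate falls to roughly 14 to 23%.
- The genotyping uses a 500K array. At a threshold of 0.0001 the one-arm rate is about 0.4 to 1.3%, and in such a screen chance findings would far outnumber this kind of error.

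Three stronger readings are tempting and not supported. First, that background markers will be reported as bupropion markers: the protocol says only that associations will be examined, in preliminary work. Second, that secondary objective 8 goes unanswered: its wording covers clinical outcomes including safety and does not require attribution to the drug. Third, that ancestry is left uncontrolled in the adverse-event analysis: Section 15.4.4 lists "options for controlling correlation of allele frequencies among members of the same subpopulation" as a feature of one of its procedures, and nothing rules out its use here.

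**Conclusion.** The point holds in a limited form. As written, the plan cannot attribute an adverse-event marker to bupropion, because it names the bupropion arm alone and no other analysis supplies the comparison. This follows from the design of the analysis and does not depend on any assumed rate.

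The size does depend on assumptions. About 60% of insomnia would be background if the smoking-cessation rates applied. A marker acting only on background insomnia would be flagged in about 24 to 39% of trials in the bupropion arm, against about 6% with the two-arm contrast. That rests on 40% carriers, at least a doubling of background risk, 100 genotyped per arm and a single test at 5%.

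The genetics work is exploratory and conditional on favorable efficacy (synopsis and Section 13.6.30). Neither the primary result nor the between-arm adverse-event table is affected. This is a minor improvement.

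**What to change.** In Section 15.4.4 and the matching sentence of the synopsis:

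1. Keep the bupropion-arm association of markers with plasma levels and with adverse events.
2. Add the same marker-by-adverse-event association in consenting placebo subjects.
3. Add a marker-by-arm contrast on the risk-difference scale, and report the marker effect in each arm beside it.
4. State that a marker will be described as predictive of bupropion safety only if the between-arm contrast supports it.

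The cost is wording and some extra analysis of data already planned, with no new samples or visits. Requiring the contrast for that claim costs power: about 35% against 54% for the drug-specific marker assumed above. For that reason the contrast should be added to the one-arm analysis and should not replace it.
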